#### 4.5.3 Laboratory assessments

- HbA1c
- Triglycerides
- HDL- / LDL-/ total serum cholesterol
- Further parameters are detailed in Section 10.2 of the CSP

Continuous laboratory values will be summarized descriptively by parameter including absolute changes from baseline. Frequency tables will be provided for qualitative data.

In addition, the frequencies for liver abnormality criteria as defined in CSP Section 10.5 will be presented:

- ALT or AST  $>3 \times ULN$ ,
- ALT or AST >3 x ULN and Total bilirubin >2 x ULN,

- ALT or AST >3 x ULN and INR >1.5 x ULN,
- ALT or AST >5 x ULN for more than 2 weeks,
- ALT or AST >8 x ULN.

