10.5 Appendix 5: Liver safety: Suggested actions and follow-up assessments

Discontinuation of study intervention for abnormal liver function should be considered by the investigator when a participant meets one of the conditions outlined in Table 10-3 or if the investigator believes that it is in best interest of the participant.

09 FEB 2023 Page: 79 of 95

Table 10-3 Liver-safety-related monitoring and discontinuation criteria

Laboratory result	Measures
ALT or AST > 3 x ULN after start of study intervention	'Close observation' as defined below
ALT or AST > 3 x ULN and TBL > 2 x ULN	Withdraw study intervention and close observation as outlined below
ALT or AST > 3 x ULN and INR > 1.5 x ULN in the absence of anti-coagulants	Withdraw study intervention and close observation as outlined below
ALT or AST > 3 ULN with appearance of fatigue, nausea, vomiting, right upper abdominal quadrant pain or tenderness, fever, rash and/or eosinophilia (> 5%)	Withdraw study intervention and close observation as outlined below
ALT or AST > 5 x ULN for more than 2 weeks	Withdraw study intervention and close observation as outlined below
ALT or AST > 8 x ULN	Withdraw study intervention and close observation as outlined below

ALT = alanine aminotransferase; AST = aspartate aminotransferase; INR= international normalized ratio, TBL = total bilirubin, ULN = upper limit of normal (all referring to serum/plasma)

In participants fulfilling one of the criteria listed in Table 10-3, investigators and participants should be alerted regarding non-specific symptoms which may be associated with liver dysfunction, including anorexia, nausea, fatigue, right upper abdominal discomfort, vomiting, malaise, jaundice, fever, and rash. Information on these symptoms should be asked for. The study participants should be reminded to contact the study site immediately, if they are concerned about such symptoms and unscheduled liver parameters should be considered. A close observation has to be initiated if any of the criteria listed in Table 10-3 occurs.

Close observation includes:

- Repeat serum chemistry panel (including serum transaminases and serum bilirubin) up to two times per week. Frequency of retesting can decrease to once a week or less if laboratory abnormalities decrease and participant is asymptomatic.
- Obtaining a more detailed history of the symptoms and prior or concurrent diseases.

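### SAP 4.5.3 omits one of the five withdrawal criteria in the liver table it cites (ALT or AST above 3 x ULN with new symptoms and/or eosinophilia), and does not declare the omission

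*SAP*

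**What the plan says.** SAP Section 4.5.3 introduces its liver table by saying that "the frequencies for liver abnormality criteria as defined in CSP Section 10.5 will be presented". Five bullets follow: ALT or AST above 3 x ULN; the same with total bilirubin above 2 x ULN; the same with raised INR; above 5 x ULN for over two weeks; and above 8 x ULN.

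The cited source, Protocol Section 10.5, Table 10-3, has six rows. The one without a counterpart in the SAP begins "ALT or AST > 3 ULN with appearance of fatigue, nausea, vomiting, right upper abdominal quadrant pain or tenderness" and goes on to fever, rash and/or eosinophilia above 5%. Its stated measure is withdrawal of study drug plus close observation.

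The INR rows also differ. The protocol has "ALT or AST > 3 x ULN and INR > 1.5 x ULN in the absence of anti-coagulants"; the SAP has "ALT or AST >3 x ULN and INR >1.5 x ULN".

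SAP Section 4.8, which lists changes to protocol-planned analyses, names only serum lipoprotein.

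**The concern.** The SAP cites a source and then does not reproduce it. The missing row is not a monitoring threshold: Table 10-3 attaches withdrawal to it, and Protocol Section 7.1.1 lists the transaminase increases of Table 10-3 among the reasons for which a participant must come off study drug.

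Liver enzyme elevation is one of the three potential risks in Protocol Table 2-2, and hepatic injury is an adverse event of special interest (AESI) under Section 8.3.6. The supporting patient study in chronic kidney disease found no evidence of hepatic toxicity, but it treated for 8 weeks against 48 here. A reader of the clinical study report will take the liver table as the complete count of participants who met the protocol's criteria. For one criterion it would give no count, and nothing would show that a row is missing.

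**Working it through.** No sample-size or probability calculation applies. The check sets the two lists side by side.

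| Table 10-3 row | Protocol measure | In SAP 4.5.3? |
|---|---|---|
| 1. "ALT or AST > 3 x ULN after start of study intervention" | Close observation | Yes |
| 2. "ALT or AST > 3 x ULN and TBL > 2 x ULN" | Withdraw | Yes |
| 3. Above 3 x ULN with INR above 1.5 x ULN, no anticoagulant | Withdraw | Yes, without the anticoagulant condition |
| 4. Above 3 x ULN with new symptoms and/or eosinophilia above 5% | Withdraw | **No** |
| 5. "ALT or AST > 5 x ULN for more than 2 weeks" | Withdraw | Yes |
| 6. Above 8 x ULN | Withdraw | Yes |

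**Counts.**
- Protocol: 6 rows = 1 close observation + 5 withdrawal.
- SAP: 5 rows = 1 close observation + 4 withdrawal.
- Missing: 5 − 4 = 1 of 5 withdrawal criteria.
- Carried over exactly as defined: 5 − 1 (omitted) − 1 (INR row reworded) = 3 of 5.

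**What the omission does inside the table.** Take two illustrative participants, both with ALT at 4 x ULN and normal bilirubin and INR. One has new nausea and fatigue; the other has no symptoms and no eosinophilia. Under Table 10-3 the first meets rows 1 and 4 (withdrawal) and the second meets row 1 only (close observation). Under SAP 4.5.3 both meet the first bullet and nothing else. The same holds for any case above 3 x ULN that stays below the other thresholds.

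**Whether the row can be derived.** Eosinophils are a protocol-required hematology test (Table 10-1), and hematology is scheduled at every visit. Symptoms are collected as adverse events (Section 8.3.1). Two details matter:
- Table 10-3 speaks of the symptoms appearing, so findings already present at baseline should not count.
- Protocol Section 10.3.3 asks sites to record the diagnosis in preference to its individual symptoms where possible. A search of adverse event terms alone could therefore miss a symptomatic case entered under a hepatic diagnosis.

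**Whether the data would reach the table.** SAP Section 4.1.1 lists unscheduled measurements but keeps them out of summary statistics and frequency tables. Protocol Sections 8.2.4 and 10.5 rely on repeat panels, up to twice weekly, after a liver finding. INR is absent from Table 10-1 and appears only in the work-up list of Table 10-4. Read literally, the SAP rule would exclude most of the values that several of these rows need.

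**The case against.** The strongest reply is that the cases are not lost. SAP Section 4.5.2 counts treatment-emergent AESIs by category and arm, hepatic injury being one category, and the protocol ties that category to Section 10.5. It also counts adverse events leading to permanent discontinuation, lists both groups individually, and gives AESI incidence by dose level. SAP Section 6.3 reports reasons for stopping treatment. This stands. A reader might infer that a participant withdrawn for symptomatic liver injury would show up nowhere except the general above-3 x ULN row; the documents do not support that. What remains is narrower: none of these outputs says which Table 10-3 criterion was met.

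A reader might also infer that the shortened INR bullet will over-count anticoagulated participants. That is largely hypothetical. INR is not a scheduled test, and under SAP Section 4.1.1 an unscheduled INR would not enter a frequency table at all. The reference to Section 10.5 could also be read as carrying the qualifier along. Exclusion criteria 11, 12 and 14 probably leave few anticoagulated participants, although anticoagulants are not on the prohibited list in Table 6-3. The INR wording deserves alignment, no more. It cannot cause the missing count either: a dropped qualifier can only widen its own row.

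Finally, it may be said that Section 4.5.3 covers laboratory data and symptoms are clinical. But eosinophilia is a laboratory value, and the SAP states no such restriction. The separate table specifications are not available here; they would not change the list written in the SAP.

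**Conclusion.** The point holds as a mismatch between the SAP and its own cited source. One of five withdrawal criteria has no row, and the change is undeclared. Within the liver table, symptomatic or eosinophilic cases below the other thresholds merge with asymptomatic ones.

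The consequence is confined to safety reporting; the primary analysis and the proof-of-concept decision are untouched. With 52 participants planned on active drug, one case is 1/52 = 1.9% of the arm. That is the weight of a single case, not a forecast: the documents give no basis for estimating how often the row would be populated, and the kidney disease study, with 184 on runcaciguat, points to few cases.

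The count of five rests on the measures printed in Table 10-3. Section 7.1.1 makes that table mandatory, while Section 10.5 asks the investigator to consider discontinuation. Those passages must be reconciled, but the omission is the same under either.

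**What to change.** Revise SAP Section 4.5.3 before unmasking:

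1. Add the sixth row: participants with ALT or AST above 3 x ULN and, within a date window fixed in the SAP, a newly appearing listed symptom and/or newly appearing eosinophils above 5%. Take symptoms from the adverse event records, including those documented with a hepatic AESI or in the reason for discontinuation, so that cases recorded under a diagnosis are not missed.
2. As a minor alignment, restore the anticoagulant condition on the INR row, using the concomitant medication dates already collected under Protocol Section 6.8.
3. State that this table uses unscheduled repeat and work-up values, as an exception to SAP Section 4.1.1.

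If the sponsor intends a table of selected laboratory thresholds only, it should say so, drop the claim that the criteria are those of Section 10.5, and declare the difference in Section 4.8. That cures the contradiction but leaves the criterion uncounted, so adding the row is preferable.

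The cost is one derived row, a date window to agree, and a small programming and review effort, including some reading of case narratives. No new data collection is needed.

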#### 4.5.4 eGFR

eGFR will be calculated using CKD-EPI formula, using the serum creatinine (SCr) concentration measured at screening. The calculation will be done by the central laboratory using the formulas specified in Table 4-1.

	SCr level at screening	Fo	ormula
Women	≤ 0.7 mg/dL	$\text{GFR} = 144 \times \left(\frac{\text{SCr}}{0.7}\right)^{-0.329}$	× 0.993 Age [× 1.159 if black]
	≤ 62 µmol/L	$\text{GFR} = 144 \times \left(\frac{\text{SCr}}{62}\right)^{-0.329}$	× 0.993 Age [× 1.159 if black]
	> 0.7 mg/dL	$\text{GFR} = 144 \times \left(\frac{\text{SCr}}{0.7}\right)^{-1.209}$	$\times 0.993^{Age}$ [× 1.159 if black]
	> 62 µmol/L	$\text{GFR} = 144 \times \left(\frac{\text{SCr}}{62}\right)^{-1.209}$	$\times 0.993^{Age}$ [× 1.159 if black]
Men	≤ 0.9 mg/dL	$\text{GFR} = 144 \times \left(\frac{\text{SCr}}{0.9}\right)^{-0.411}$	× 0.993 Age [× 1.159 if black]
	≤ 80 µmol/L	$\text{GFR} = 144 \times \left(\frac{\text{SCr}}{80}\right)^{-0.411}$	× 0.993 Age [× 1.159 if black]
	> 0.9 mg/dL	$\text{GFR} = 144 \times \left(\frac{\text{SCr}}{0.9}\right)^{-1.209}$	$\times 0.993^{Age}$ [× 1.159 if black]
	> 80 µmol/L	$\text{GFR} = 144 \times \left(\frac{\text{SCr}}{80}\right)^{-1.209}$	$\times 0.993^{Age}$ [× 1.159 if black]

#### Table 4-1: Formula for eGFR calculation

 $GFR = glomerular filtration rate in mL/min/1.73 m^2$ , eGFR = Estimated glomerular filtration rate, SCr = Serum creatinine

The eGFR values based on serum creatinine are assumed to be log-normally distributed and will be summarized descriptively including relative changes from baseline with 95% CI. The eGFR values will be summarized using summary statistics as defined for log-normally distributed variables.

Geometric mean eGFR including one SD range over time will be plotted. Individual plots of eGFR values will also be presented by stratum (DRSS at baseline) and treatment group.

A frequency table will be presented summarizing decreases in eGFR values from baseline by >50%, >40%, >30%, etc. including cumulative frequencies. Decrease in eGFR [%] will be calculated as 1- (eGFR post-dose / eGFR at baseline) \*100.

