7.1.2 Temporary discontinuation

Treatment should be withheld temporarily if any of the following conditions apply:

- Relevant hypotension or tachycardia considered to be related to treatment with runcaciguat, e.g. SBP < 90 mmHg with symptoms of hypotension persisting > 24 hours, or AE indicating non tolerability with regard to mode of action (e.g. severe dizziness, orthostatic dysregulation, syncope). In case of additional, subsequent temporary discontinuation(s), the investigator should consider whether a permanent discontinuation of the study intervention is appropriate.
- Temporary discontinuation for drop in eGFR from baseline: If the participant presents a decrease of eGFR ≥ 40% compared with baseline, the investigator should temporarily discontinue study intervention and perform confirmatory laboratory examinations. If eGFR decrease by ≥ 40% is confirmed, study intervention should be discontinued permanently (see Section 7.1.1). If the re-assessed laboratory result indicates a decrease in eGFR <40% from baseline, study intervention may be re-started at the same dose as before this temporary discontinuation, in line with section 7.1.3. The investigator should consider a close observation of the case (e.g. repeated laboratory investigation of renal function).

- The investigator may decide to temporarily discontinue treatment for other reasons if deemed appropriate for the safety and well-being of the participant.

A temporary discontinuation exceeding 14 consecutive days or 21 days overall results in a permanent discontinuation (see section 7.1.1)

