In case of clinically relevant abnormal laboratory results, the investigator has the discretion to perform unscheduled repeat laboratory examinations earlier than at the intervals provided in the SoA in Section 1.3. These unscheduled examinations should be processed by the central lab to ascertain that the data will be included in the database. At the investigator's discretion, additional laboratory parameters may be investigated and samples may be processed by the local lab. In case of relevant liver enzyme elevation (see also Section 10.5), the investigator should perform a repeat serum chemistry panel 2 times per week (including serum transaminases [AST and ALT] and serum bilirubin), frequency of retesting can decrease to once a week if laboratory abnormalities decrease and participant is asymptomatic.

Estimation of glomerular filtration rate (eGFR)

eGFR will be calculated using CKD-EPI formula, using the serum creatinine concentration measured at screening (Kidney Disease: Improving Global Outcomes (KDIGO) CKD Work Group 2013). The calculation will be done by the central laboratory. In case of a decrease by \geq 40%, a critical alert will be provided to the investigator, as it may represent a reason for treatment discontinuation, as described in Section 7.1.2.

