#### 4. Statistical Analyses

#### 4.1 General Considerations

#### 4.1.1 General Principles

The SAP will be finalized prior to unmasking.

The statistical evaluation will be performed by using the software SAS (release 9.4 or higher; SAS Institute Inc., Cary, NC, USA) and R (version 3.5.2 or higher; R Foundation for Statistical Computing, Vienna, Austria).

All data will be listed and summarized in tables. Graphical illustrations will be provided by treatment group (runcaciguat, placebo) where appropriate. Summary statistics will be presented for the participants treated with runcaciguat and for the participants treated with placebo. Descriptive statistics by visit will be provided for the original data as well as for change from baseline, where applicable. Additional summary statistics per dose of runcaciguat administered will be presented, where meaningful. Doses may be grouped to reach more meaningful sample sizes. Frequency tables will be provided for qualitative data.

Continuous variables assumed to be normally distributed will be summarized using the number of participants, mean, standard deviation, minimum, lower quartile, median, upper quartile and maximum. The geometric mean and SD will be provided additionally for the variables where log-normal distributions are assumed.

Generally, data will be analyzed comparing the two intervention groups against each other.

Furthermore, for the runcaciguat treatment group, summary statistics by visit for continuous variables will be further broken down by the actual maintenance dose level, i.e., the dose level reached after the end of the titration phase (at Visit 6) (in case a sufficient number of patients pertains to this dose level).

Data from unscheduled measurements will be listed, but not included in summary statistics or frequency tables.

Listings will be provided sorted by treatment group (runcaciguat, placebo), DRSS at baseline (47, 53) and participant identifier.

Baseline is defined as the last pre-dose assessment before first study intervention.

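### SAP 4.5.4 misplaces a bracket in the percent-decrease expression and ties eGFR to screening creatinine; programmed literally, falls in eGFR could be understated

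*SAP*

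**What the plan says.** **Percent decrease.** SAP 4.5.4, in the text after Table 4-1, plans this table: "A frequency table will be presented summarizing decreases in eGFR values from baseline by >50%, >40%, >30%, etc. including cumulative frequencies". The quantity behind it is defined as "Decrease in eGFR [%] will be calculated as 1- (eGFR post-dose / eGFR at baseline"; the bracket then closes and a multiplication by 100 follows.

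**Source of creatinine.** SAP 4.5.4 says: "eGFR will be calculated using CKD-EPI formula, using the serum creatinine (SCr) concentration measured at screening". It adds that the central laboratory does the calculation with the formulas in Table 4-1. The column of that table that selects the formula is headed "SCr level at screening". The cut-points are 0.7 mg/dL for women and 0.9 mg/dL for men, with a shallow exponent at or below the cut-point and a steep one above. Protocol 8.2.4 has the same phrase, "using the serum creatinine concentration measured at screening", in the paragraph that sets up the laboratory's alert for a decrease of 40% or more.

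**What depends on eGFR.** Protocol 7.1.2 acts on a fall from baseline: "If the participant presents a decrease of eGFR ≥ 40% compared with baseline". Protocol 8.3.6 and SAP 4.5.2 define acute kidney injury of special interest by either a 2.0-fold rise in creatinine or an eGFR fall above 50%. SAP 4.1.1 gives the reference point: "Baseline is defined as the last pre-dose assessment before first study intervention".

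**The concern.** Under ordinary operator precedence the decrease expression subtracts a percentage from 1, so it cannot fill the rows it was written for.

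The screening wording cannot be reconciled with the rest of the same section, which plans eGFR over time, relative change from baseline and a post-dose value. It also sits badly with the baseline definition, since biochemistry is repeated before dosing at Visit 2. The natural repair is to put the visit's creatinine into Table 4-1. That still leaves the exponent chosen by the screening value if the column heading is followed, and the resulting numbers would look plausible.

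Renal impairment is a listed risk in protocol Table 2-2. Protocol 2.3.1 reports acute kidney injury in 2.7% on runcaciguat against 1.7% on placebo in the earlier kidney-disease study. The 40% alert, the interruption rule, the eGFR criterion for kidney injury and the SAP table all need a correctly calculated eGFR.

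**Working it through.** The documents report no numerical eGFR result, so there is no stated figure to reproduce. The check is to evaluate the rules as printed.

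**1. Percent decrease.** Let r = post-dose eGFR / baseline eGFR.

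- As printed: 1 - r × 100.
- As the [%] label and the categories require: (1 - r) × 100.

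| r | True fall | As printed | Bracket moved |
|---|---|---|---|
| 1.0 | 0% | -99 | 0 |
| 0.7 | 30% | -69 | 30 |
| 0.6 | 40% | -59 | 40 |
| 0.5 | 50% | -49 | 50 |
| 0.2 | 80% | -19 | 80 |
| 0.01 | 99% | 0 | 99 |
| 0 | 100% | 1 | 100 |

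The two differ by a constant: (1 - r) × 100 - (1 - 100r) = 99. The printed value is positive only when r is below 0.01, and its maximum is 1. No participant can enter a row above 30, 40 or 50%.

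**2. Creatinine and exponent.** From Table 4-1, eGFR is proportional to (SCr / k)^a.

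- Men: k = 0.9; a = -0.411 at or below k, -1.209 above.
- Women: k = 0.7; a = -0.329 at or below k, -1.209 above.

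The constant and any race factor cancel in a ratio within one participant, as does the age term if age is held fixed. The creatinine values below are illustrative and are not in the documents.

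*Screening creatinine used throughout:* the post-dose value equals the screening value, so every fall is 0%.

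*Man, 0.85 to 1.5 mg/dL (1.76-fold):*
- Exponent from the visit: (1.5/0.9)^-1.209 / (0.85/0.9)^-0.411 = 0.5392 / 1.0238 = 0.527, a fall of 47.3%.
- Exponent fixed by screening: (1.5/0.85)^-0.411 = 0.792, a fall of 20.8%.

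*Woman, 0.65 to 1.15 mg/dL (1.77-fold):*
- Exponent from the visit: 0.5487 / 1.0247 = 0.535, a fall of 46.5%.
- Exponent fixed by screening: (1.15/0.65)^-0.329 = 0.829, a fall of 17.1%.

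In both examples the correct fall exceeds 40% while the fixed-exponent fall does not. The 2.0-fold creatinine criterion is not met. The eGFR criterion of more than 50% is not met on either calculation, so what is at risk here is the 40% alert and rule, not the event of special interest.

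*Creatinine rise needed for a 40% fall:*
- Exponent fixed by screening: (1/0.6)^(1/0.411) = 3.47-fold in men; (1/0.6)^(1/0.329) = 4.72-fold in women.
- Exponent from the visit, starting at the cut-point: (1/0.6)^(1/1.209) = 1.53-fold.

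*Rise needed for a 50% fall, visit exponent, starting at the cut-point:* 2^(1/1.209) = 1.77-fold. At the cut-point, the eGFR criterion for kidney injury therefore adds to the creatinine criterion only for rises between 1.77-fold and 2.0-fold.

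*Participant above the cut-point at screening:* a doubling gives 1 - 2^-1.209 = 56.7% on either calculation, so there is no effect.

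**3. Boundary.** The SAP row is above 40%; protocol 7.1.2 and 8.2.4 use 40% or more. A fall of exactly 40% meets the protocol's condition but does not enter the SAP row, even with the bracket corrected.

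**The case against.** The case for treating both as drafting slips is strong.

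- **Bracket.** The intent is plain from the [%] label and the categories. Literal output of -99 for a participant with no change would be noticed at once. The expression feeds one descriptive table. The relative-change summaries (SAP 4.1.9), the eGFR plots, the alert, the interruption rule and the events of special interest do not use it. All of this stands.
- **Screening wording.** An alert for a decrease, a confirmatory re-test and eGFR over time are impossible without on-treatment creatinine. The phrase may come from the eligibility criterion, which does use eGFR at screening. This also stands: a reader might infer that eGFR could never change on treatment, but the documents rule that out as the intended meaning.
- **Size.** The understated falls need a mixed reading, visit creatinine with the screening exponent, that neither document states in full. They arise only at or below the cut-point at screening. This stands as a limit on the size.

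A reader might also infer that renal safety signals would be missed. The documents do not support that. Creatinine is in the biochemistry panel at every visit, investigators must review each laboratory report, and a doubling of creatinine qualifies as kidney injury whatever the eGFR. For example, a man going from 0.85 to 1.7 mg/dL shows 24.8% on the fixed exponent against 54.7%, yet meets the creatinine criterion either way.

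What the objection does not remove is the shared dependence. The safeguards avoid the percent-decrease expression, but those based on eGFR do not avoid the eGFR calculation: SAP 4.5.4 assigns it to the central laboratory under Table 4-1, and under protocol 8.2.4 that laboratory's eGFR drives the 40% alert.

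**Conclusion.** Both errors are in the current text, and each gives a wrong result if followed literally.

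The bracket error empties one descriptive table, would be obvious on output, and goes no further. The creatinine wording matters more because its mixed form is not self-revealing: it can turn a fall of 46 to 47% into one of 17 to 21% and so fail to reach 40%. That holds only for men at or below 0.9 mg/dL or women at or below 0.7 mg/dL at screening whose creatinine later crosses the cut-point. The figures rest on illustrative creatinine values and on Table 4-1 as printed; its coefficients were not checked against an outside source.

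The supported conclusion is that renal signals could be understated if the text is programmed literally, not that they would be missed. The laboratory's own specification is not in the documents and may already be correct.

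**What to change.** 1. In SAP 4.5.4, write the decrease as (1 - eGFR post-dose / eGFR at baseline) × 100.
2. In SAP 4.5.4 and protocol 8.2.4, state that each eGFR uses the creatinine of that visit. Name the creatinine that serves as baseline, consistent with SAP 4.1.1.
3. Head the selecting column of Table 4-1 so that the exponent follows the same creatinine value that enters the formula.
4. Check the central-laboratory specification for both the eGFR calculation and the 40% alert. If it used a screening-fixed exponent, recalculate the affected values.
5. Reconcile the SAP row for falls above 40% with the protocol's condition of 40% or more, so that the table and the rule count the same participants.

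The cost is a few words in two sections, one column heading and one query to the laboratory. Items 1 to 4 change no clinical threshold. Item 5 asks only that the two documents agree.
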